5.4 Drug Accountability

The pharmacy clinical trials team must maintain accurate accountability records including, but not limited to, the number of bottles/tablets received, the number of bottles/tablets and bottle numbers (i.e., unique treatment pack number) dispensed to each participant, batch number, expiry date, and the date of the transaction in addition to the quantity of investigational product returned by each patient. A Sponsor accountability log (includes both inventory/subject level details) will be provided to study sites.

Participants will be asked to return any unused IMP and/or empty packaging at each study visit. The study drug returns will be returned to pharmacy by the research team

for accountability. The returns will be verified by the pharmacy clinical trials team and the Clinical Research Associate (CRA)/dedicated research member prior to disposal at site. Destruction of IMP must be in accordance with the site IMP destruction Standard Operating Procedure (SOP). Disposal of IMP is only permitted with sponsor authorisation.

The pharmacy clinical trials team are required to maintain copies of study drug shipping receipts and drug accountability records in accordance with regulatory requirements.

5.5 Storage of IMP

The IMP must be stored at room temperature, between 15°C to 25°C, in a secure area with limited access. Protect from moisture.

Appropriate storage conditions must be ensured by completion of temperature logs in accordance with local requirements. As a minimum requirement, min/max thermometers readings must be recorded each day of the working week, Mondays to Fridays. The temperature logs can be stored centrally, and records made available for review to the sponsor CRA as requested.

If the IMP is exposed to temperatures outside of 15°C to 25°C, all supplies must be quarantined and the CRA emailed immediately, copying in the Trial Manger. Await further instruction from the Sponsor.

5.6 Subject Compliance

All participating patients will be instructed about the importance of medication compliance. Compliance with treatment will be monitored at every follow up visit and patients will be asked to bring back their empty medication packaging. Remaining tablets will be counted by the treating physician and will be recorded in the patient CRF.

Patients should be informed to contact the trial teams in case of accidental medication loss.

All patients will be asked not to modify the treatment without discussion. If a patient intends to interrupt treatment with IMP, they will be asked to contact the trial team prior to doing so. If a patient decides to stop the treatment without speaking to any trial members, this will be recorded at the next follow up appointment. The patient will remain in the study unless they chose to formally withdraw from the study.

5.7 Concomitant Medication

We are proposing a study of hydroxychloroquine in addition to their usual medication in women with underlying aPL who are planning pregnancy. As with chloroquine, antacids may reduce absorption of hydroxychloroquine, so we advise a four hour interval between the IMP and the intake of any antacids. As hydroxychloroquine may enhance the effects of a hypoglycaemic treatment, a decrease in doses of insulin or antidiabetic drugs may be required.

All patients will very likely be on some form of medications prior to entering this trial, which may include aspirin, heparin, in some particular cases warfarin or immunosuppressant medications such as azathioprine. (Warfarin may be used as secondary thrombosis prevention, however, once they have a positive pregnancy test, the warfarin will be stopped and they switched to low molecular heparin according to usual medical practice). An individual assessment will be made prior to entering the trial. None of those drugs are contraindicated as concomitant therapy with hydroxychloroquine. All drugs patients are taking will be recorded at every visit in the patient CRF. This information includes drug type, strength, how long the medication was taken for and the indication.

Patients participating in this trial will either be planning for or be pregnant. All medications absolutely contraindicated in pregnancy should be avoided after pregnancy is confirmed. In this particular patient group this may for example include anticoagulation treatment (such as warfarin) or certain types of blood pressure medications.

6 Selection and Withdrawal of Subjects

6.1 Inclusion Criteria

- Women with known aPL (ie. isolated aPL or APS) who are planning pregnancy. aPL are defined by the presence of a positive test for anticardiolipin antibodies (IgG/IgM isotypes > 95th percentile) and/or lupus anticoagulant and/or anti- beta 2 glycoprotein-I (IgG/IgM isotypes > 95th percentile), on two or more consecutive occasions more than 12 weeks apart (a positive aPL test is defined under 'glossary and definitions'). The last positive test must be within 12 months of study entry.
- 2. Written informed consent to participate

6.2 Exclusion Criteria

- 1. Women who are already pregnant
- 2. Allergy or adverse event to hydroxychloroquine. Hypersensitivity to the active substance, 4-aminoquinoline or any of the compounds of the IMP or placebo.
- 3. Current treatment with hydroxychloroquine
- 4. Age < 18 or > 45
- 5. Body weight < 45 kg
- 6. Psoriasis
- 7. Uncontrolled epilepsy
- 8. Anti-Ro antibodies
- 9. Renal replacement therapy
- 10. Other severe active co-morbidities (HIV, hepatitis B, severe gastrointestinal, neurological or blood disorders)
- 11. Porphyria

- 12. History of retinopathy or newly diagnosed retinopathy
- 13. History of galactose intolerance, lactase deficiency or glucose-galactose malabsorption
- 14. History of glucose-6-dehydrogenase deficiency
- 15. Participation in any other IMP trial at the time of consent
- 16. Previous pregnancy failure on hydroxychloroquine

6.3 Selection of Participants

Definitions used in the HYPATIA study:

- Screening: Time from consent to randomisation
- Baseline visit: Randomisation to treatment arm/Initial IMP dispensation
- Pre-pregnancy study visits: Visits between randomisation and achieved pregnancy
- Pregnancy study visits: Study visits on routine follow up visits

Potentially eligible women will be identified in routine outpatient clinics. Patients will receive full information about the HYPATIA study, and if they decide to take part written informed consent will be obtained. Patients will have as much time as they need to consider their participation. Eligibility will be assessed and provided all eligibility criteria are fulfilled, study randomization can be undertaken and the IMP can be dispensed (baseline visit) (see trial flow chart).

Once a woman is enrolled into the HYPATIA study, she will attend follow up visits every three months until she falls pregnant (at 3, 6, 9 and 12 months, defined as prepregnancy visits) in addition to her usual standard pregnancy care.

If no pregnancy is achieved in the 12 months from entering the study, this will be recorded in the study CRF and the study medication will be stopped. Once a woman has been enrolled into the HYPATIA study and has started taking the IMP, she will have a blood test including full blood count, kidney function and liver function every three months during the pre-pregnancy period and during pregnancy (these tests will coincide with her follow up visits) and are to ensure that it is safe to take the IMP (hydroxychloroquine).

On these visits the IMP will be repeatedly dispensed and compliance will be assessed. This will be documented in medical records and recorded in the eCRF.

When a woman falls pregnant she will contact the study team and will attend her first pregnancy visit (1st trimester visit). At this visit a new trial medication will be dispensed.

Follow up visits for the HYPATIA study purpose will be scheduled once every trimester (defined as 1st, 2nd and 3rd trimester visits), however, if the participant required closer monitoring she will be followed up accordingly as per standard of care. Women will be instructed to stop trial medication on the day of delivery and will be asked to hand in the rest of the trial medication at their post-partum follow up. The post-partum visit shall be completed 6 weeks post-partum. For some women it may be difficult to attend a follow up visit within 6 weeks after delivery (due to sleep deprivation or other challenges with a newborn) and the study teams can therefore contact the patient post-delivery to collect outcome data (date of delivery & information about the child). This can be decided on an individual basis.

All eligible women will have been diagnosed with persisting antiphospholipid antibodies (aPL) prior to trial entry. Results of aPL, i.e. anticardiolipin IgG and IgM antibodies, beta2glycoptroteinI IgG and IgM antibodies and lupus anticoagulant, confirming their presence or a diagnosis of APS. For the purpose of the HYPATIA study the last positive test must be within 12 months of study entry. The dates when the tests were performed routinely at the trial sites have to be documented in the notes and recorded in the eCRF.

Patients with anticardiolipin (IgG or IgM) antibodies and/or beta2glycoptroteinI (IgG or IgM) antibodies above the 95th percentile are considered positive and the levels will be recorded in the CRF. Each site will be asked about their local normal ranges (i.e. the local cut off for the 95th percentile) for anticardiolipin (IgG or IgM) antibodies and/or beta2glycoptroteinI (IgG or IgM) antibodies, which also have to be recorded in the patient notes and eCRF.

For the purpose of the HYPATIA study blood test results from prior to entering the trial can be used and for the purpose of the HYPATIA study with two specifications:

- the last positive aPL test result must be within 12 months of study entry
- Other blood results such as full blood count, kidney and liver function must be within 3 months of study entry.

We accept past positive antiphospholipid antibody screens as valid, as long as they have a positive screen within 12 months of study entry and if there is physical evidence of such in the patients' records.

6.4 Randomisation Procedure / Code Break

Written informed consent to enter the trial and to be randomized must be obtained from each patient, after explanation of the aims, methods, benefits and potential hazards of the trial and before any trial procedure is conducted.

It must be made completely and unambiguously clear that the patient is free to refuse to participate in all or any aspect of the trial, at any time and for any reason, without incurring any penalty or affecting their treatment.

Signed consent forms must be kept by the investigator and documented in the medical records and a copy given to the patient, with another copy filed in medical records. Upon consent, a letter should be sent to the general practitioner informing him/her of the trial and the participant's involvement in it.

Women with aPL are usually considered as having high-risk pregnancies and are monitored closely during pregnancy. For the purposes of HYPATIA study, we would expect patients to be seen for a minimum number of visits as indicated in section 4.2. Women who decide to participate in the HYPATIA trial will have their usual care plus HCQ or placebo in addition to their usual medication. Women recruited at selected centres will be invited to have a blood sample taken once at baseline, prior to pregnancy, once every trimester and post-partum for additional research. These samples will be analyzed for biomarkers and for pharmacokinetics of hydroxychloroquine in pregnancy.

Funding for the above studies will be obtained separately.

6.4.1 Randomisation

Randomisation will be undertaken by the local research team at each site once written informed consent has been obtained, eligibility confirmed, and baseline data collected.

Randomisation is by the method of minimisation, balanced by thrombosis (yes/no), previous adverse pregnancy outcomes (yes/no), previous pregnancy (yes/no), refractory obstetric APS (yes/no) and center.

Randomisation will be performed via a bespoke web-based randomisation system hosted by the King's College London, Clinical Trials Unit (KCTU). This system can be accessed 24 hours a day. Authorised site staff will be allocated a username and password for the system by the Trial Manager. If new staff members join the study, a user-specific username and password must be requested via the Trial Manager from the KCTU team and a request for access to be revoked must be requested when staff members leave the project. Study site staff experiencing issues with system access or functionality should contact the Trial Manager in the first instance.

Once eligibility has been confirmed by recruiting sites, authorised site staff will log into the system by going to www.ctu.co.uk and clicking the link to access the randomisation system. A full audit trail of data entry will be automatically date and time stamped, alongside information about the user making the entry within the system. Staff will enter key information about the patient, including the unique Participant Identification Number (PIN) generated from the Elsevier MACRO electronic data capture (EDC) system after consent. Once a patient is randomised, study drug will be automatically allocated in the system and confirmation emails will be sent to relevant personnel, with appropriate information.

If there are any difficulties in accessing this KCTU website, investigators should call the number below.

https://ctu.co.uk

Telephone: [name] (or e-mail: [contact] or [contact]>)

The investigator, research team, site pharmacy team and the trial manager will be kept blind to the treatment allocation.

Unique pack numbers will be generated for the active and placebo products and will be sent with randomization emails. The trial statistician will know only A vs B, with the meaning of A & B held by the KCTU.

Detailed description of the randomization process: The IMP pack details will be uploaded to the randomization system so the system will know what the production pharmacy has available centrally.

For any site the trial manager will order the IMP packs as required. That will generate an email with specific pack numbers to be sent to site via the study manufacturing pharmacy at GSTT. Once the IMP has arrived at the requested study site, the trial manager will mark them as 'received'. Then, when a patient is randomized at that site, the system will automatically select a pack in the right trial arm and that pack number will be on the confirmation email, so it can be prescribed. When a patient comes in for follow up, the site will go into the system and allocate a new pack for them and the system will select one in the same trial arm.

6.4.2 Emergency Code Break

All participants will remain blind to treatment allocation until the primary analyses are complete and the primary paper has been accepted. Sites will be informed of the participants treatment allocation at this point.

Treating physicians should only request emergency code break when information about the participant's trial treatment is necessary for the appropriate medical management of the participant and where stopping the blinded medication is not sufficient. The treating physician or investigator will have the primary right to break the blind in any moment in case of emergency and they will be able to unblind immediately and without delay.

The HYPATIA Trial has commissioned a 24-hour telephone-based emergency code break service, Emergency Scientific Medical Services (eSMS). Participants will be asked to carry emergency cards during the study, which will have details of the code break telephone number. The code break number will also be printed on the study medication bottles. The caller can request code break from eSMS using either the IMP treatment bottle number or the participants study PIN, which is allocated by the MACRO eCRF system after consent.

ESMS will notify the Danish Sponsor of any code break requests received, irrespective of outcome. The Sponsor will inform the Principal Investigator of instances of unblinding. This will be recorded and the trial statistician informed at the analysis stage of the trial.

6.5 Withdrawal of Subjects

In consenting to the HYPATIA trial, patients are consenting to trial treatment, trial follow-up and data collection. However, an individual patient may stop treatment early or be stopped early for any of the following reasons:

- drug intolerance
- any change in the patient's condition that justifies the discontinuation of the treatment in the clinician's opinion
- withdrawal of consent for treatment by the patient

As the patient's participation in the trial is entirely voluntary, they may choose to discontinue the trial treatment at any time without loss of benefits to which they are otherwise entitled. Although the patient is not required to give a reason for discontinuing their trial treatment, a reasonable effort should be made to establish this reason while fully respecting the patient's rights.

Patients who withdraw from the treatment will be asked to remain in the trial for the purpose of follow-up and data analysis (unless the patient withdraws their consent from all stages of the trial). If a patient decides to withdraw from the HYPATIA study no further data can be collected, however data collected until the point of withdrawal will be retained. If a patient decides to only withdraw from treatment, data and adverse events will be followed up. Adverse events will be followed up regardless of the IMP status until the end of the trial.

In the specific circumstance when a patient would like to withdraw from the trial, but allows us to collect the results of the pregnancy and data on the child from medical notes without contacting her, a consent form 2 has to be signed. In such case only the pregnancy outcome data will be collected following the withdrawal and adverse events will not be reported.

The investigator also has the right to withdraw patients from the study drug in the event of inter-current illness, adverse events (AEs), serious adverse events (SAE's), Suspected Unexpected Serious Adverse Reaction (SUSAR's), protocol violations, cure, administrative reasons or other reasons.

If the rare event occurred that women develop abnormal creatinine clearance of 30ml/min women will be withdrawn from the trial.

It is understood by all concerned that an excessive rate of withdrawals can render the study un-interpretable; therefore, unnecessary withdrawal of patients should be avoided. Patients who withdraw from the study will not per se be replaced. However, this decision will be left to the discretion of the Data Monitoring Committee.

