No formal interim analyses are planned. The Data Monitoring Committee will aim to meet in person at least every 6 months, and will consider the results so far. They are empowered to request that the trial stops if there is overwhelming evidence for or against one treatment are such that to randomize further patients would be unethical.

• Procedures for dealing with missing data, unused data and false data. False data may be e.g. interpolated data, and it is not necessarily false

We will follow a four point framework for dealing with incomplete observations which will allow the correct method to be chosen and subsequently implemented.

1. Attempt to follow up all randomized participants, even if they withdraw from allocated treatment

2. Perform a main analysis of all observed data that is valid under a plausible assumption about the missing data. Specifically, we will assume data is missing at random (MAR). Under this assumption, imbalances between treatment groups due to dropout can be corrected by appropriate multiple regression models.

3. Perform a sensitivity analyses to explore the effect of departures from the assumption made in the main analysis. The MNAR (missing not at random) analysis will use the method of White et al. (2011) [28] as implemented in the Stata command rctmiss.

4. Account for all randomized participants, at least in the sensitivity analyses

This framework highlights the importance of using plausible assumptions with regards to the nature of the missing data. These assumptions will then be tested using appropriate sensitivity analyses on observed data using complete cases analysis. For the purpose of the main analysis we will make the assumption that missing data is missing at random and the effect of the intervention is the same in those with and without the observations. Furthermore, checks will be made to ensure that the percentage of missing data within each treatment allocation is not significantly different.

We do not intend to create false data. No duly randomized subjects with outcome data will be excluded. All relevant data collected will be used.

• Procedures for reporting deviations from the original statistical plan

It is not intended to deviate from the data analysis plan as agreed; but if it should prove necessary, the nature, reasons and implications of such deviations for interpreting the results, will be reported to the funders and in any subsequent publications.

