10.2 Sample Size

The sample size was calculated based on our audit data.

Retrospective data from St Thomas' Hospital showed that treatment with HCQ was associated with a higher rate of live birth (67% in women with SLE and aPL treated with HCQ versus 57% in women in the control group p=0.005) and a lower prevalence of aPL related pregnancy morbidity (47% versus 63% p=0.004).

The HCQ intervention will be added to current standard of care. The trial is powered to detect a 16% reduction in pregnancy morbidity, which is the main outcome of the study (total sample size 328). A minimum of 328 women will therefore be randomized. In order to achieve a number of 328 pregnant women, we will randomize 400 patients. This takes into account those women who do not achieve pregnancy within 12 months and those who do not pregnant due to other reasons.

The calculation was made on the following: significance alpha = 0.05, power 1-beta 80%, percentage cross 5%.

11 Trial Steering Committee

A HYPATIA steering committee has been appointed. The committee includes [name], [name], [name], further HYPATIA study team members and a lay person. A dedicated person from the Clinical Trials Unit will be appointed. An independent chair will be appointed.

The overall role will be to provide overall supervision of the HYPATIA study and the steering committee will meet on a 6 monthly basis. The Steering Committee is the main decision making body. It has overall responsibility for scientific strategy and direction and has ultimate responsibility for ensuring the project's aims are delivered on time and within budget.

12 Data Monitoring Committee

A Data Monitoring Committee has been appointed. The committee includes an independent chair, an independent statistician, the trial statistician and an independent expert.

The DMC has decided the following stopping rules:

Confirmed option of unblinding available at any stage, BUT only if concern that treatment will clearly harm or benefit patients

The simple rule of 3 standard errors will be applied to difference between groups.

13 Direct Access to Source Data and Documents

The Investigator(s) will permit trial-related monitoring, audits, REC review, and regulatory inspections by providing the Sponsor(s), Regulators and REC direct access to source data and other documents (e.g. patients' case sheets, blood test reports, X-ray reports, histology reports etc.).

14 Ethics & Regulatory Approvals

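### Whether withdrawn women are replaced is left to the Data Monitoring Committee, which sees the difference between groups; a body blind to outcome by arm should decide (minor)

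*Protocol*

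**What the plan says.** Section 6.5 (Withdrawal of Subjects) sets a default, "Patients who withdraw from the study will not per se be replaced", and then qualifies it: "However, this decision will be left to the discretion of the Data Monitoring Committee". It gives no criterion, no timing and no condition on what the committee may look at when it decides.

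The same committee has access to comparative results. Section 10.1 states: "The Data Monitoring Committee will aim to meet in person at least every 6 months, and will consider the results so far". Section 12 gives its stopping rule: "The simple rule of 3 standard errors will be applied to difference between groups". Section 12 also lets it unblind: "Confirmed option of unblinding available at any stage, BUT only if concern that treatment will clearly harm or benefit patients". Its membership is described thus: "The committee includes an independent chair, an independent statistician, the trial statistician and an independent expert". Section 6.4.1 adds that the trial statistician knows the arms only as A and B.

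On error control, section 10.1 says "No formal interim analyses are planned" and sets the final significance level at 5% with no adjustment. Section 10.2 fixes the target at 328 pregnant women from 400 randomised. It explains the difference by women who do not become pregnant and does not name withdrawal. Section 11 says of the other oversight body: "The Steering Committee is the main decision making body".

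**The concern.** Replacing or not replacing withdrawals changes how many women contribute to the primary analysis. The protocol gives that choice to the committee that must look at the between-group difference in order to apply its own stopping rule. A/B labelling does not help, because the size of the difference is visible under any labels.

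A sample size that may respond to the interim effect does not keep the nominal 5% level in general, and the final test makes no allowance for it. Even if the committee acts neutrally, neutrality could not be shown afterwards, and an extension agreed late in a close trial would invite challenge. The access to comparative data is also unnecessary here: whether withdrawals have left the trial short can be judged from pooled counts.

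**Working it through.** **Inputs from the protocol.** Event rates 63% and 47%, alpha 0.05, power 80%, 5% crossover, 328 pregnant women, 400 randomised (section 10.2); final level 5% (section 10.1).

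**Assumptions.** Two-sided alpha and 1:1 allocation, since neither is stated. The number replaced, W, is taken as 16, 33 or 66, about 5%, 10% and 20% of 328, because the protocol gives no withdrawal rate.

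**Step 1: the plan's own sample size.** Per arm, n = [1.96·√(2·p̄·q̄) + 0.842·√(p₁q₁ + p₂q₂)]² / (p₁ − p₂)². With p̄ = 0.55 this is [1.96·√0.495 + 0.842·√0.4822]² / 0.16² ≈ 150.6, so 151 per arm and 302 in total. With a continuity correction it is 163 per arm, 326 in total. Without the correction but with 5% crossover in one arm it is 334 to 336. The stated 328 is consistent with the last two, and nothing in this point changes it.

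**Step 2: model of the decision.** Without replacement the analysis has 328 − W women; with replacement it has 328. Under the null hypothesis, z-statistics on nested samples of sizes m < N are bivariate normal with correlation √(m/N).

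**Step 3: one decision during the trial.** Let z₁ be the statistic on m women, where m is 50%, 75% or 90% of 328 − W. The conditional chance of rejecting at final size N, with t = m/N, is

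CE(z₁, N) = 1 − Φ[(1.96 − √t·z₁)/√(1 − t)] + Φ[(−1.96 − √t·z₁)/√(1 − t)].

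The worst case always takes the larger of CE(z₁, 328 − W) and CE(z₁, 328), averaged over the standard normal distribution of z₁. If N is fixed in advance the same calculation returns 0.0500, as it should.

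**Step 4: decision after a full test.** If the test is run on all 328 − W women and replacements are added only when it is not significant, the error is 1 − P(|Z₁| ≤ 1.96 and |Z₂| ≤ 1.96), with correlation √((328 − W)/328).

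| W replaced | Step 3, 50% of data | Step 3, 75% | Step 3, 90% | Step 4: correlation | Step 4: error |
|---|---|---|---|---|---|
| 16 | 5.1% | 5.2% | 5.3% | √(312/328) = 0.975 | 6.0% |
| 33 | 5.2% | 5.4% | 5.6% | √(295/328) = 0.948 | 6.5% |
| 66 | 5.5% | 5.8% | 6.1% | √(262/328) = 0.894 | 7.1% |

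If replacement is instead taken to add W women on top of 328, the step 4 values are slightly lower: 6.0%, 6.4% and 6.9%.

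**Step 5: direction.** Replacing after a promising look does not always favour rejection. With 246 women observed and W = 33, moving from 295 to 328 changes the conditional one-sided error from 0.219 to 0.211 at z₁ = 1.8, but from 0.005 to 0.014 at z₁ = 1.0. At z₁ = 1.8 replacement lowers the chance of a false positive; at lower z₁ it raises it.

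**The case against.** The case for leaving the text alone has real substance.

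- **The discretion is narrow.** The default is no replacement, and the number added cannot exceed the number withdrawn. The surrounding text in section 6.5 is about excessive withdrawal making the study hard to interpret. Nothing says the committee should use effect data for this decision. This stands, and it limits the size of the problem.
- **Few withdrawals need cost an outcome.** Under section 6.5, women who stop treatment are asked to stay in follow-up, and those leaving the trial may sign a second consent form so that pregnancy outcome is still collected. Some withdrawals will also occur before pregnancy, so they do not map one-to-one onto the 328. The assumed 16 to 66 may therefore be generous.
- **A charter may settle it.** That is possible, but the protocol states the rule itself and points to no such limit. The objection does not remove the point.

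Two stronger readings are tempting and are not supported. A reader might infer that the true error rate is 6% to 7%. That needs a complete final test first and replacements afterwards. With up to 21 months from entry to delivery (section 6.6), recruitment would have to reopen after follow-up of the other women had ended, and the protocol plans no such sequence. A reader might also infer that the trial statistician's seat on the committee puts an unblinded final analyst in charge of sample size. The protocol does not say outright who runs the final analysis, and section 6.4.1 limits this person to A and B labels. Those labels do not hide the size of the difference, but they belong in any fair account.

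**Conclusion.** The point holds as a minor one. The protocol gives a sample-size decision, without a criterion, to the committee that sees the comparative results, and the final 5% test makes no allowance for this. Under deliberate steering of one decision at 50% to 90% of the data, the two-sided error is at most about 5.3% for 16 replacements, 5.6% for 33 and 6.1% for 66. A committee acting in good faith would produce less. These bounds rest on assumed numbers of replacements, a two-sided test and the normal approximation. They are separate from any effect of the three-standard-error stopping rule. The stronger reason to change the text is credibility: the final number of women should be demonstrably independent of the observed effect.

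**What to change.** In section 6.5, replace the sentence that gives the Data Monitoring Committee discretion with:

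> Whether recruitment is extended to replace withdrawals is decided by the Trial Steering Committee, blind to outcome by arm, using only the pooled number of pregnant women with a primary outcome against the target of 328; the DMC takes no part in this decision.

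The condition of being blind to outcome by arm should stay in, because the steering committee includes study team members (section 11). No sentence on analysing withdrawn women in their randomised group is needed; sections 6.5 and 10.1 largely cover that already.

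The cost is one protocol sentence and matching wording in any committee charters. There are no extra patients or visits, and 328 is unchanged. The one small downside is that the Data Monitoring Committee loses a discretion it does not need; its power to recommend stopping is untouched.
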